- p. 12-lead ECG assessments will be performed after the participant has been at rest for approximately 3 minutes. At Screening, the average of 3 consecutive ECGs collected 1 to 2 minutes apart will be used to determine participant eligibility; at Baseline, only 1 reading is required for determination of eligibility. At approximately 2 hours following dosing at weekly time points, single 12-lead ECGs will be obtained. Additional ECGs can be performed at the investigator's discretion (eg, if abnormalities are noted).

- q. At Screening and Baseline, blood pressure and heart rate assessments should be performed in order to confirm eligibility (see Exclusion Criterion in [Section 5.2](#)). Triplicate supine heart rate and blood pressure measurements should be taken at approximately 1-minute intervals predose (Day 1 only, Baseline), and at approximately 2 hours after dosing on Day 1 and Weeks 1 through 6. The triplicate supine heart rate and blood pressure measurements will be followed by a single measurement after approximately 2 minutes in a standing position to allow for orthostatic assessments. Additional time points can be added at the investigator's discretion (eg, if abnormalities are noted). Further details are provided in [Section 8.2.3](#) and in the Operations Manual.
- r. The "Baseline/Screening" C-SSRS form will be completed for all participants at Screening to determine eligibility and the "Since Last Visit" C-SSRS form will be completed at Baseline to ensure that the participant continues to qualify for the trial. The "Since Last Visit" C-SSRS form will also be completed at weekly time points after Baseline.
- s. EPS assessments can be completed at any time during the trial, per investigator discretion, if symptoms are present.
- t. Prior and concomitant medications should be recorded from Screening through the participant's last visit/contact.
- u. Adverse events (serious and nonserious) should be recorded from the first dose of IMP through the participant's last visit/contact.
- v. The Week 6 prolactin results will be partially blinded; the investigator will be notified if the prolactin levels exceed a predefined limit with instructions to send the participant for appropriate follow-up.
- w. For women of childbearing potential only. Pregnancy tests can be performed at any time during the trial at the discretion of the investigator if pregnancy is suspected. Any urine pregnancy tests that are positive must be confirmed using a serum test.

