2.3 Benefit/Risk Assessment

This trial is designed primarily to evaluate the efficacy and safety of 2 fixed doses (15 mg QD and 30 mg QD) of emraclidine in the target patient population.

Based on results from Part B of Trial CVL-231-SCH-001, treatment with 30 mg QD emraclidine in patients with schizophrenia experiencing an acute exacerbation of psychosis may be beneficial based on clinically meaningful reductions from Baseline in PANSS and CGI-S scores (see [Section 2.2.3](#)).

Doses were chosen for this trial based on nonclinical safety and toxicology data and clinical safety data available to date (see [Section 4.3](#)).

There is a potential for an increase in blood pressure and heart rate based on nonclinical findings and findings from the single and multiple ascending dose trials (see [Section 2.2.2](#) and [Section 2.2.3](#)). The cardiovascular effects of emraclidine will be carefully monitored on an inpatient basis throughout the trial. The inpatient design will also facilitate careful monitoring of participants during and subsequent to washout from their antipsychotic drug treatment.

More detailed information about the known and expected benefits and potential risks of emraclidine are found in the Investigator's Brochure.

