5.4 Screen Failures

Screen failures are defined as participants who consent to participate in the clinical trial but are not subsequently randomly assigned to IMP. A minimal set of screen failure information is required to ensure transparent reporting of screen failure participants to meet the Consolidated Standards of Reporting Trials publishing requirements and to respond to queries from health authorities. Minimal information includes demography, screen failure details, and eligibility criteria.

Individuals who do not meet the criteria for participation in this trial (screen failure) at screening may be rescreened once at the discretion of the investigator and after consultation with the medical monitor unless screen failure is due to a positive urine drug screen for illicit substances. Rescreened participants will be assigned a new participant number.

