6.7.2 Prohibited Therapy

All participants must agree to discontinue all prohibited medications during the Screening Period in order to meet the protocol-specified washout periods. [Table 4](#) provides the required duration of washout for selected prohibited medications. All other prohibited medications must be discontinued at least 24 hours before the first dose of IMP.

Table 4 List of Medications Prohibited Before Randomization

Prohibited Prior Medications	Washout (if applicable)
Antipsychotic agents	
Oral (or immediate-release intramuscular) aripiprazole or cariprazine	14 days
Other oral (or immediate-release intramuscular) antipsychotic agents	7 days
Depot or long-acting injectable antipsychotic agents	1.5 cycles (per prescribing information)
Antidepressants	
Fluoxetine or Symbax	28 days
Monoamine oxidase inhibitors	14 days
Citalopram and escitalopram	7 days
Venlafaxine and desvenlafaxine	7 days
All other antidepressants	14 days
Mood stabilizers (ie, lithium and/or anticonvulsants)	14 days
All other psychoactive substances (except benzodiazepines)	7 days
Varenicline (eg, Chantix)	7 days
Beta receptor antagonists to treat hypertension	Not applicable
Other antihypertensive agents	Not applicable
Receiving more than 2 medications to treat hypertension	
Have not been on stable doses of antihypertensive medications for >3 months	

[Table 5](#) lists all medications prohibited during the trial, including exceptions, where appropriate.

Table 5 List of Medications Prohibited During the Treatment Period

Psychotropic agents including, but not limited to, the following:
a) Antipsychotics, including depot or long-acting injectable formulations
b) Antidepressants (including monoamine oxidase inhibitors)
c) Mood stabilizers (ie, lithium and/or anticonvulsants)
d) Benzodiazepines, except specific benzodiazepines when used to treat anxiety, agitation, or insomnia secondary to schizophrenia ^a
e) Prescription stimulants (including appetite suppressants and treatments for attention-deficit hyperactivity disorder or narcolepsy)
f) Opioid analgesics, unless approval is obtained from the medical monitor. Approval for opioid use may be considered for a documented and clinically appropriate indication (eg, episodic pain, tooth extraction) if prescribed at a medically appropriate dose and frequency
Hypnotics, including ramelteon and other non-benzodiazepine sleep aids, except for specific medications when used to manage active insomnia ^b

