The BARS ([Barnes, 1989](#)) consists of 4 items related to akathisia: objective observation of akathisia by the investigator, subjective feelings of restlessness by the participant, subjective distress due to akathisia, and global clinical assessment of akathisia. The first 3 items are rated on a 4-point scale, with a score of 0 representing absence of symptoms and a score of 3 representing a severe condition. The global clinical evaluation is made on a 6-point scale, with a score of 0 representing absence of symptom and a score of 5 representing severe akathisia. To complete this scale, participants are observed while they are seated and then standing for a minimum of 2 minutes in each position.

Symptoms observed in other situations (eg, while engaged in neutral conversation or engaged in other activity) may also be rated. Subjective phenomena are to be elicited by direct questioning.

8.3 **Adverse Events, Serious Adverse Events, and Other Safety Reporting**

The definitions of AEs and SAEs can be found in [Section 10.3](#). Definitions of AESIs are provided in [Section 8.3.7](#).

Adverse events will be reported by the participant (or, when appropriate, by a caregiver, surrogate, or the participant's legally authorized representative). The investigator and any qualified designees are responsible for detecting, documenting, and recording events that meet the definition of an AE, SAE, or AESI and remain responsible for following up AESIs and AEs that are serious, considered related to the IMP or trial procedures, or that caused the participant to discontinue IMP (see [Section 7.1](#)).

Further details about AE recording and follow-up are provided in [Section 10.3](#).

8.3.1 *Time Period and Frequency for Collecting AE and SAE/AESI Information*

All AEs and SAEs/AESIs will be recorded from the first dose of IMP until follow-up contact at the time points specified in the Schedule of Assessments ([Section 1.3](#)).

Medical occurrences that begin before the start of IMP dosing but after obtaining informed consent will be recorded as medical and/or psychiatric history.

All SAEs/AESIs will be recorded and reported to the sponsor or designee immediately and under no circumstance should this exceed 24 hours, as indicated in [Section 10.3](#). The investigator will submit any updated SAE/AESI data to the sponsor or designee within 24 hours of it being available.

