### 5.15.1. Adverse Events

Adverse events will be mapped to MedDRA version 26.0 or higher preferred term and system organ class. If a subject experiences multiple events that map to a single preferred term, the greatest severity and strongest investigator assessment of relation to IMP will be assigned to the preferred term for the appropriate summaries. Events with missing severity or relationship will be classified as outlined in [Section 3.2.1](#). Summaries of treatment-emergent AEs will include any AEs reported beginning with the initiation of study drug on Day 1 through the follow up contact. An overall summary of TEAEs, including the number of subjects with a TEAE, TEAE related to IMP, AESI, serious TEAE, serious TEAE related to IMP, TEAE leading to discontinuation of

IMP, and TEAE leading to death will be summarized. [REDACTED]

[REDACTED] The occurrence of treatment emergent adverse events (TEAEs) will be summarized by treatment group using preferred terms, system organ classes, and severity. Separate summaries of TEAEs, treatment-emergent serious adverse events (TESAEs), TEAEs related to IMP, AESIs, events leading to discontinuation of IMP will be generated by system organ class and preferred term.

Treatment-emergent adverse events with  $\geq 2\%$  incidence in either one of the emraclidine arms and a greater incidence than the placebo arm will be summarized by preferred term. The most common TEAEs in either one of the emraclidine arms, defined as an incidence  $\geq 5\%$  and greater than 2 times of the incidence in the placebo group, will also be summarized by treatment group using preferred term. [REDACTED] All

adverse events reported will be listed for individual subjects showing both verbatim and preferred terms. All adverse events that occurred prior to the initiation of study treatment will be excluded from the tables but will be included in the listings.

Missing onset dates will be imputed as previously outlined in [Section 4.1.12](#) as required to determine treatment-emergent events.

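### Serious events between consent and first dose, the window that holds the required antipsychotic washout, are not collected, reported or tabulated as AEs or SAEs

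*Protocol*

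**What the plan says.** Recording starts at first dose. Protocol Section 8.3.1 states: "All AEs and SAEs/AESIs will be recorded from the first dose of IMP until follow-up contact". Footnote u of the Schedule of Assessments (Section 1.3) repeats this and names both classes of event: "Adverse events (serious and nonserious) should be recorded from the first dose of IMP through the participant's last visit/contact".

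For the interval between consent and first dose, Section 8.3.1 says: "Medical occurrences that begin before the start of IMP dosing but after obtaining informed consent will be recorded as medical and/or psychiatric history". Footnote j of the Schedule gives the same rule. Neither makes an exception for serious events.

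Washout takes place in that interval. Section 6.7.2: "All participants must agree to discontinue all prohibited medications during the Screening Period in order to meet the protocol-specified washout periods". Section 2.3 recognises that this needs watching: "The inpatient design will also facilitate careful monitoring of participants during and subsequent to washout from their antipsychotic drug treatment". Screening lasts up to 15 days, or up to 21 with medical monitor approval (Section 4.1.1).

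For people who consent but are not randomized, Section 5.4 sets the required data: "Minimal information includes demography, screen failure details, and eligibility criteria".

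SAP Section 5.15.1 writes as if pre-dose AEs will exist: "adverse events that occurred prior to the initiation of study treatment will be excluded from the tables but will be included in the listings".

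**The concern.** Stopping antipsychotics in people admitted for an acute exacerbation is something the trial asks of them. Harm that follows is a risk of taking part, whether or not the person is later dosed. Under the recording rule, a serious event that begins in that window is handled as background history. Nobody has to judge whether it was caused by washout, and the sponsor need not hear of it within 24 hours. It also falls outside every safety table, because the safety set is randomized and dosed participants only (Protocol Section 9.2, SAP Section 5.15).

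The gap is widest where it matters most. A serious event in washout tends to end eligibility. Suicidal behavior on the C-SSRS is Exclusion Criterion 10, risk of violent behavior is an example under Exclusion Criterion 30, and a rise in PANSS total above 120 at Baseline fails Inclusion Criterion 4. Such a participant becomes a screen failure, the group for which least must be kept. At stake is the sponsor's and the ethics committee's view of the risk of a procedure that the protocol itself requires.

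**Working it through.** **Is a washout event an AE or SAE under the protocol?**

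1. Section 10.3.1 (Table 8) ties an AE to the use of trial intervention. Section 6 says that the trial interventions are the IMPs. An event before any IMP does not fit the definition.
2. Section 10.3.2 says that an event which is not an AE cannot be an SAE, even if it meets a seriousness criterion.
3. Section 8.3.1 and footnotes j and u set the same boundary by date.
4. Grading and causality (Table 12) and 24-hour reporting (Section 8.3.1, Table 14) apply to AEs, SAEs or AESIs. So none of them applies to a serious event with onset in washout.

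**Where does the event end up?**

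- *Randomized participants:* in history, which SAP Section 5.7 codes, summarizes by treatment group and lists.
- *Screen failures:* SAP Section 5.1 lists all data collected from anyone who consents, but a listing shows only what was collected. Section 5.4 does not name SAEs or history. SAP Table 3 assigns patient history listings to the ITT set (randomized only) and gives all screened subjects disposition, eligibility and demography outputs.
- *The pre-dose AE listing in SAP Section 5.15.1:* the protocol collects no AEs before first dose, so this listing would have little or nothing to show.

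**How many people could be affected?**

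The concern rests on no figure that the plan states for washout. The plan's enrolment figures are consistent: 279 completers / (1 − 0.25) = 372 randomized.

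- Planned screen failures: 600 − 372 = 228, and 228 / 600 = 38%.
- Scale of pre-dose time, if all 600 stayed 15 days and all 372 were treated for 45 days: 600 × 15 = 9,000 days and 372 × 45 = 16,740 days; 9,000 / (9,000 + 16,740) = 35%.
- With 7 pre-dose days each: 4,200 / (4,200 + 16,740) = 20%. With the exceptional 21 days each: 12,600 / (12,600 + 16,740) = 43%.

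These shares give a sense of scale only. Many screen failures will leave early, and some treated participants will discontinue.

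The documents give no washout event rate. As an assumption only, take a serious event in 0.5% to 2% of those who consent:

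- among 600: 600 × 0.005 = 3 to 600 × 0.02 = 12 events;
- among 228, at equal risk: 228 × 0.005 = 1.1 to 228 × 0.02 = 4.6 events.

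**The case against.** The strongest reply is that much of this harm leaves a trace.

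- *History is kept.* This stands for randomized participants. History carries no required causality assessment or expedited report.
- *Harm that starts or worsens after first dose is an AE* (Protocol Table 9, SAP Section 3.2.1.2), even if washout caused it. This stands in full.
- *SAEs learned of after discharge and considered related to trial participation must be notified* (Section 8.3.1), and Section 10.1.1 has the investigator notify the IRB/IEC of SAEs and other significant safety findings as that body requires. These may catch some events. Neither clearly covers an event seen on the unit during Screening.
- *The Baseline C-SSRS looks back over the interval since Screening, and reasons for screen failure are tabulated* (SAP Section 5.6). The C-SSRS covers suicidality only, and at Baseline only those who get that far. A failure reason may name the event, but Section 5.4 asks for no seriousness, causality or outcome.
- *Section 5.4 sets a minimum, and the history rule has no screen-failure exception.* This is true, so a site may record the event. The text does not make clear that it must.
- *Starting at first dose is a deliberate and consistently stated choice.* It suits TEAE tables. It is a weaker reason for not collecting SAEs during a required procedure.

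A reader might also infer that Section 8.3.1 contradicts Section 8.3, under which investigators "remain responsible for following up AESIs and AEs that are serious, considered related to the IMP or trial procedures". The documents do not support that. The sentence covers events that meet the AE, SAE or AESI definition, and procedure-related AEs after dosing satisfy it.

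**Conclusion.** The gap is real and bounded. Serious events with onset between consent and first dose are not collected, assessed for causality, reported within 24 hours or tabulated as AEs or SAEs. In randomized participants they appear only as history. For screen failures even that is not clearly required.

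Three stronger readings are tempting and should not be drawn:

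- *That serious washout harm never reaches the safety data.* History is coded, summarized and listed for randomized participants, and harm that begins or worsens after first dose is an AE.
- *That 228 people go through washout with no record.* The 228 (38%) is an upper bound. It includes people who fail on entry scores, ECG, laboratory tests or drug screen, and the documents do not say how many begin washout.
- *That participants spend 21 days in unrecorded washout.* Twenty-one days is the Screening limit with approval, not the washout length. Table 4 gives 7 days for most oral antipsychotics, 14 days for two of them, and 1.5 cycles for depot products.

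The expected event counts rest on an assumed rate and show only that a few events are plausible. The point concerns participant safety and oversight. The efficacy inference is untouched.

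**What to change.** 1. In Protocol Section 8.3.1 and Schedule footnotes j and u (repeated in SAP Section 9.1), collect and report SAEs, and AEs judged related to trial procedures including washout, from ICF signing for everyone who consents. Other pre-dose occurrences can stay in history.
2. Word the AE definition in Section 10.3.1 so that these events qualify. Otherwise Section 10.3.2 would still rule them out as SAEs.
3. Add SAEs to the screen-failure minimum data in Section 5.4.
4. In SAP Section 5.15.1, keep TEAE tables from first dose, and show pre-dose events as a separate period for all who consented, so that the listing matches what the protocol collects.

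The cost is protocol and SAP wording, some extra SAE reports and the related site work. Alpha, power, sample size and TEAE tables are unchanged.

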8.3.7 Adverse Events of Special Interest

All AESIs should be reported according to the procedures and timelines for SAEs (see [Section 10.3.4](#)).

The following events will be reported as AESIs:

- AEs that result in the discontinuation of IMP including those resulting from elevations in liver test results (see [Section 10.6](#))
- Heart rate >120 bpm
 - Confirm heart rate by ECG
 - Repeat heart rate measurement 30 and 60 minutes after participant is at rest
 - Report as an AESI and notify the medical monitor if heart rate remains >120 bpm 60 minutes after initial elevation OR if it is not sinus tachycardia
 - Continue to follow the participant as clinically appropriate
- QTcF is >500 ms or the QTc value represents a >60 ms increase from Baseline
 - Repeat ECG
 - Report as an AESI and notify the medical monitor
 - Repeat ECGs every 30 minutes until QTcF <450 ms or improves to <30 ms from baseline value
 - Continue to follow the participant as clinically appropriate if QTcF does not improve
- Systolic blood pressure reading (average of triplicates) ≥160 mmHg but <200 mmHg and/or diastolic blood pressure reading ≥100 mmHg but <120 mmHg
 - Repeat blood pressure measurements after 5 minutes of participant at rest in a quiet room. If blood pressure (average of triplicates) reading continues to be ≥160 mmHg systolic and/or ≥100 mmHg diastolic, additional blood pressure measurements should be performed after 30 minutes and 60 minutes from the initial elevation
 - If blood pressure elevation continues to be ≥160 mmHg systolic and/or ≥100 mmHg diastolic 60 minutes after initial elevation, report as an AESI and notify the medical monitor
 - Withhold IMP

- Consider referring participant to a health care facility for further evaluation and treatment as appropriate
- Resume IMP only upon consultation with the medical monitor
- Systolic blood pressure ≥ 200 mmHg and/or diastolic blood pressure ≥ 120 mmHg
 - Repeat blood pressure measurements after 5 minutes of participant at rest in a quiet room. If blood pressure (average of triplicates) reading continues to be ≥ 200 mmHg systolic and/or ≥ 120 mmHg diastolic, additional blood pressure measurement should be performed after 30 minutes from the initial elevation
 - If blood pressure continues to be ≥ 200 mmHg systolic and/or ≥ 120 mmHg diastolic after 30 minutes from initial elevation, report as an AESI and notify the medical monitor
 - If blood pressure does not improve, perform a physical examination and obtain the following tests: serum blood urea nitrogen, creatinine, serum cystatin-C, plasma renin activity, serum catecholamines (metanephhrines, normetanephhrines), serum aldosterone, endothelin level; urinalysis; and an ECG
 - Refer participant to a health care facility for further evaluation, monitoring, and treatment.
 - Withhold IMP
 - IMP may be resumed only after discussing with the medical monitor

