16.	
Positive drug screen or a positive test for alcohol (note: individuals who test positive for alcohol may be rescreened).
 
Participants with a positive urine drug screen resulting from use of marijuana (any THC-containing product), prescription, or over-the-counter medications or products that, in the investigator's documented opinion, do not signal a clinical condition that would impact the safety of the participant or interpretation of the trial results may continue evaluation for the trial following consultation and approval by the medical monitor.

17.	
Any of the following clinical laboratory test results at the Screening Visit, confirmed by a single repeat measurement, if deemed necessary:
 
 • AST or ALT $\geq 2 \times$ ULN • Total bilirubin $>1.5 \times$ ULN. If Gilbert's syndrome is suspected, total bilirubin $>1.5 \times$ ULN is acceptable if the conjugated or direct bilirubin fraction is $<20\%$ of total bilirubin
18.	
Positive pregnancy test result prior to receiving IMP.
 
Note: female participants who are pregnant, breastfeeding, or planning to become pregnant during IMP treatment or within 7 days after the last dose of IMP are also excluded.

Other Exclusionary Safety Assessments	
19.	
12-lead ECG demonstrating any of the following at the Screening Visit and at Baseline:
 
 • QTcF interval >450 ms • QRS interval >120 ms (unless right bundle branch block) • PR interval >200 ms • LVH with ST depressions and/or T wave inversions in leads with relatively tall R waves (ie, LVH with associated ST-T wave abnormalities) • Type 2 second-degree or third-degree atrioventricular block • Heart rate <45 bpm or >100 bpm • Abnormal ECG changes (such as clinically significant ST depression or elevation or T wave inversion) • Abnormal heart rhythm (atrial fibrillation and atrial flutter) 
Note: at Screening, eligibility will be based on the average of a centrally read triplicate set of ECGs.
 
At Baseline Visit, if any of the above criteria are met on the machine read of the ECG, the medical monitor should be consulted to determine whether the participant is eligible for randomization.
 
The medical monitor should be contacted in any instance where the investigator is uncertain regarding the interpretation of ECG results.

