Electrocardiogram recordings will be obtained after the participant has been supine and at rest for approximately 3 minutes. Additional 12-lead ECGs may be obtained at the investigator's discretion and should always be obtained in the event of an early termination. The ECG results will be evaluated at the investigational site to determine the participant's eligibility and to monitor safety during the trial. The principal investigator (or qualified designee) will review, sign, and date each ECG reading, noting whether or not any abnormal results are of clinical significance. The ECG will be repeated if any results are considered to be clinically significant. Any clinically significant changes occurring during the trial will be recorded in the AE section of the eCRF. A central ECG service will be used for reading all ECGs in order to standardize interpretations for the safety analysis. Additional guidance on collection of ECGs will be provided in the Operations Manual.

At Screening, triplicate 12-lead ECGs are required to assess participant eligibility. A triplicate set of ECGs is 3 consecutive ECGs collected 1 to 2 minutes apart over a 5-minute period. If, during screening, according to the investigator's judgment, any abnormal ECG finding is deemed medically significant (impacting the safety of the participant or the interpretation of the trial results) or meets an exclusion criterion (see [Section 5.2](#)), the participant should be excluded from the trial. The central ECG service will provide the QTcF corrections and average of the 3 ECGs performed to determine eligibility.

At all other specified time points in the Schedule of Assessments ([Section 1.3](#)) where an ECG recording must be performed, only a single ECG is required.

Exclusion criteria for screening do not apply as mandatory discontinuation criteria for participants who are already randomized. A repeat ECG should be performed in case of any clinically significant abnormality that is identified in a randomized participant during the treatment period and, in these cases, the medical monitor should be consulted on the appropriateness of the participant continuing in the trial.

8.2.5 *Clinical Safety Laboratory Assessments*

See [Section 10.2](#) for the list of clinical laboratory tests to be performed and the Schedule of Assessments ([Section 1.3](#)) for the timing and frequency.

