Investigators are not obligated to actively seek AEs, AESIs, or SAEs after conclusion of the trial participation. However, if the investigator learns of any SAE, including a death, at any time after a participant has been discharged from the trial, or AESI, and he/she considers the event to be related to the IMP or trial participation, the investigator must promptly notify the sponsor.

8.3.2 *Method of Detecting AEs and SAEs/AESIs*

The method of recording, evaluating, and assessing causality of AEs and SAEs/AESIs and the procedures for completing and transmitting SAE/AESI reports are provided in [Section 10.3](#).

Care will be taken not to introduce bias when detecting AEs and/or SAEs/AESIs. Open-ended and nonleading verbal questioning of the participant is the preferred method to inquire about AE occurrences.

8.3.3 *Follow-up of AEs and SAEs/AESIs*

After the initial AE/SAE/AESI report, the investigator is required to proactively follow each participant at subsequent visits/contacts. All SAEs/AESIs will be followed until resolution, stabilization, the event is otherwise explained, or the participant is lost to follow-up (as defined in [Section 7.3](#)). Further information on follow-up procedures is given in [Section 10.3](#).

8.3.4 *Regulatory Reporting Requirements for SAEs/AESIs*

Prompt notification by the investigator to the sponsor regarding an SAE/AESI is essential so that legal obligations and ethical responsibilities towards the safety of participants and the safety of an IMP under clinical investigation are met.

The sponsor has a legal responsibility to notify both the local health authority and other health authorities about the safety of an IMP under clinical investigation. The sponsor

will comply with country-specific regulatory requirements relating to safety reporting to the health authority, IRBs/IECs, and investigators.

Investigator safety reports must be prepared for suspected unexpected serious adverse reactions according to local regulatory requirements and sponsor policy and forwarded to investigators as necessary.

An investigator who receives an investigator safety report describing an SAE/AESI or other specific safety information (eg, summary or listing of SAEs/AESIs) from the sponsor will review, acknowledge, and then file it along with the Investigator's Brochure and will notify the IRB/IEC, if appropriate, according to local requirements.

8.3.5 *Pregnancy*

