#### 4.1.6. Baseline Value

For purposes of analysis, the baseline value is defined as the last value obtained prior to initiation of IMP. Should the Day 1 visit value be obtained after the first dose of IMP or if this value is not available at Day 1, then the most recent value obtained prior to earliest initiation of IMP will be used for the baseline value. For ECGs, baseline is the last non-missing value obtained prior to the initiation of IMP. If the last non-missing value is obtained at the screening visit, then the baseline is the average of the triplicates. For vital signs taken in triplicate, the baseline value will be defined as the average of the predose values on Day 1 (calculated separately for each collection position, if applicable). If the triplicate value is not available, then the last non-missing value obtained prior to the initiation of IMP will be used.

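### Protocol 8.3.7: for baselines below 390 ms, the ECG that triggers the QTc AESI can already meet the stop condition for the 30-minute ECG series

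*Protocol*

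**What the plan says.** Protocol 8.3.7 defines the QTc AESI by two limbs, one absolute and one relative: "QTcF is >500 ms or the QTc value represents a >60 ms increase from Baseline". The second limb has no minimum absolute value and does not name the QT correction.

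Four actions follow. The first is a repeat ECG, with no condition attached. The second, also unconditional, is "Report as an AESI and notify the medical monitor". The third is the timed series: "Repeat ECGs every 30 minutes until QTcF <450 ms or improves to <30 ms from baseline value". The fourth is "Continue to follow the participant as clinically appropriate if QTcF does not improve".

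Three other places bear on the point:

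- Exclusion Criterion 19 (Protocol 5.2) lists "QTcF interval >450 ms" as exclusionary and sets no lower bound, so short baseline values are eligible.
- SAP 4.1.6 fixes the reference value: "For ECGs, baseline is the last non-missing value obtained prior to the initiation of IMP".
- Protocol 8.3.3 sets the general duty for AESIs: "All SAEs/AESIs will be followed until resolution, stabilization, the event is otherwise explained, or the participant is lost to follow-up". Protocol 8.2.4 adds, for the treatment period: "A repeat ECG should be performed in case of any clinically significant abnormality that is identified in a randomized participant", with medical monitor consultation.

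**The concern.** A change-from-baseline trigger matters most for participants whose QTcF starts low, because they can have a large rise without approaching an absolute limit. In this rule an absolute stop limit of 450 ms can end the serial ECGs for some of those participants before a second timed tracing is taken.

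The other measurement-based AESIs in 8.3.7 are built differently. Heart rate and blood pressure are re-measured at set times and judged against the limit that raised the alert. Only the QTc item can stop on a limit unrelated to the limb that fired.

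What is at stake is documentation of recovery on a fixed schedule. The 30-minute series is the only timed QTc follow-up in the protocol. Otherwise the next scheduled tracing is the weekly single ECG at about 2 hours after dosing (Protocol 1.3, footnote p). Sites may also read the rule differently and act differently.

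**Working it through.** The plan states no figure to reproduce, so this is a logic check of two rules, followed by a range for an assumed baseline distribution.

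**Inputs.** Let b be baseline QTcF and q the on-treatment QTcF, in ms, reading QTc in the second trigger limb as QTcF.

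- Trigger (8.3.7): q > 500, or q − b > 60.
- Stop (8.3.7): q < 450, or q − b < 30.
- Eligibility (5.2): b of 450 or less, with no floor.

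**Can trigger and stop hold on the same ECG?**

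- Trigger by q > 500: the first stop limb fails. The second needs b > q − 30 > 470, which eligibility excludes. No overlap.
- Trigger by q − b > 60: the second stop limb fails, since the rise exceeds 30. The first holds when q < 450. Both rules are then true when b + 60 < q < 450, which requires b < 390.

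**Example.** With b = 375 and q = 440, the rise is 65 ms, so the trigger is met. Because 440 < 450, the stop condition is met too. If the unconditional repeat ECG also reads 440 ms, it confirms a persistent 65 ms rise and again satisfies the stop condition. Reading the series as requiring at least one 30-minute tracing does not help: a value of 440 ms there ends it.

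**Width of the window, in whole ms.**

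- b = 350: q from 411 to 449
- b = 370: q from 431 to 449
- b = 380: q from 441 to 449
- b = 388: q = 449 only
- b = 389 or more: none

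Enumerating b = 300-450 and q = 300-600 gives 4,005 overlapping pairs, which matches 89 × 90 / 2. All arise from the >60 ms limb. The count shows the shape of the region; it is not a probability.

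**Alternative readings.** If each stop limb is matched to the trigger limb in the same position, or if both stop limbs are required, the overlap is 0 pairs. The unpaired or is the sole cause.

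**Share with b < 390.** The documents give no QTcF distribution. Assume a normal baseline truncated at 450 ms, so that the share is Φ((390 − mean)/SD) / Φ((450 − mean)/SD):

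| Assumed mean | SD 15 | SD 20 | SD 25 |
|---|---|---|---|
| 395 ms | 36.9% | 40.2% | 42.7% |
| 405 ms | 15.9% | 22.9% | 28.4% |
| 415 ms | 4.8% | 11.0% | 17.3% |

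The range is about 5% to 43%.

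**Correction named.** The first trigger limb, the stop rule, eligibility and SAP 5.15.5 all use QTcF; the >60 ms limb says QTc. As an illustration, a raw QT of 360 ms at 90 bpm (RR = 0.667 s) gives 360/0.667^(1/3) ≈ 412 ms by Fridericia and 360/0.667^(1/2) ≈ 441 ms by Bazett, a gap of 29 ms. Protocol 2.2.3 reports heart-rate increases on emraclidine, so the choice of correction is not neutral.

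**The case against.** The strongest reply is that little is lost. The stop condition qualifies only one of the four listed actions. The repeat ECG, AESI report and medical monitor notice are unconditional, and the line on continued follow-up carries no 450 ms limit, so it covers someone still 65 ms above baseline. Sections 8.3.3 and 10.3.3 require follow-up to resolution or stabilization, and 8.2.4 requires a repeat ECG for significant abnormalities. All of this stands. A reader might infer that follow-up never starts for these participants; the documents do not support that. What these provisions lack is an ECG interval, so they do not replace the timed series.

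It is also fair to say that a sensible site would match the limbs in order, absolute with absolute and change with change. That reading removes the overlap, but the text does not state it.

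A reader might also object that a participant with a 450 ms baseline who exceeds 500 ms may leave the series at 479 ms, since 479 − 450 = 29 ms. That exit is stated, is not met on the triggering ECG, and contradicts nothing. Whether it is acceptable is a clinical judgement. Strict pairing would be a clinical choice too: the same participant would have to fall below their own baseline before the series ended.

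On the QT correction, the trigger sentence opens with QTcF, and the central ECG service supplies QTcF corrections for the screening ECGs (8.2.4). The documents do not show that sites would use another formula on treatment. The wording mismatch remains.

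Finally, the triggering ECG at about 2 hours is already close to the median Tmax reported in 2.2.3 (1.0-1.8 hours fasted, 3.0 hours fed). The likelier loss is timed documentation of recovery rather than of the peak.

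**Conclusion.** The point holds in a limited form. Read literally, the rule defeats itself in one window: baseline below 390 ms, a rise above 60 ms, and QTcF still below 450 ms. There the 30-minute series need not start although the rise is unresolved. Low-baseline participants who reach 450 ms or more, and everyone who triggers above 500 ms, stay in the series.

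The 5-43% rests on assumed means and SDs. It is the share who could be exposed if such a rise occurred, not the share who would be. Multiplying it by 372 would count people with low baselines, about a third of them on placebo, and not people affected. Rises of this size are expected to be rare: Protocol 2.2.2 reports no QTc change in the dog studies, and 2.2.3 reports no clinically meaningful ECG change other than heart rate in participants with schizophrenia.

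The planned QTcF summaries are defined independently of the rule: SAP 5.15.5 counts any post-baseline occurrence by category. This is a safety-monitoring wording defect that should be corrected.

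**What to change.** The sponsor should reconcile the trigger and stop wording of the QTc item in Protocol 8.3.7 so that the ECG that raised the AESI cannot already satisfy the stop condition. The >60 ms limb should name the same correction, QTcF, as the rest of the rule and the SAP. The numeric limits, and how the stop condition relates to each trigger limb, are for the sponsor to decide.

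The edit is about one sentence, carried in a protocol amendment with the ethics review that 10.1.1 requires. The SAP needs no change. The running cost is a few extra repeat ECGs in participants who are already inpatients.
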